3.2.2.4. Duration of Response

Duration of response (DOR) is defined as the time from date of the first radiographic response (CR or PR) to the earliest documented disease progression or death due to any cause.

3.2.2.5. Progression-free Survival

Progression-free survival (PFS) is defined as the time from date of the first dose of study treatment to the earliest documented disease progression by Investigator assessment, or death due to any cause, whichever occurs first. If a patient has not had a PFS event at the time of the analysis cutoff or at the start of any new anticancer therapy, PFS is censored at the date of last adequate tumor assessment.

3.2.2.6. Overall Survival

Overall survival (OS) is defined as the time from date of the first dose of study treatment to the date of death due to any cause. If a death has not been observed by the date of the analysis cutoff, OS will be censored at the date of last contact.

3.2.3. Other Secondary Endpoints

3.2.3.1. Pharmacokinetic Endpoints

- Plasma concentration-time profiles and PK parameter estimates for encorafenib and its metabolite LHY746, and binimetinib and its metabolite AR00426032.

CCI [REDACTED]

- [REDACTED]
- [REDACTED]
- [REDACTED]
- [REDACTED]
- [REDACTED]

3.3. Baseline Variables

The date of first dose of study treatment is the earliest date of non-zero dosing of any study drug. The date of last dose of study treatment is the latest date of non-zero dosing of any study drug.

Baseline is defined as the last completed assessment performed prior to the first dose date/time. If an assessment that is planned to be performed prior to the first dose of study treatment per the protocol is performed on the same day as the first dose of study drug and the time is unknown, it will be assumed that it was performed prior to study treatment administration and will be considered as baseline assessment.

[REDACTED]

[REDACTED]

Unscheduled assessments may be considered baseline assessment if they meet the criteria above. Data reported at the End of Treatment (EOT) visit are not eligible for baseline selection. The ECG baseline will be the average of triplicate ECG measurements obtained before the start of treatment on cycle 1 day 1.

3.4. Safety Endpoints

Safety endpoints will be summarized based on the on-treatment period unless otherwise specified. Safety data collected outside the on-treatment period will be listed but not summarized.

3.4.1. Adverse Events

An AE is considered a treatment-emergent adverse event (TEAE) if the event starts on or after the first dosing day and time/start time, if collected, but before the last dose +30 days, or start of subsequent anticancer *drug* therapy minus 1 day, whichever occurs first. Any events that started prior to date of the first dose are not considered TEAEs. If an AE starts on the same day as date of the first dose, it will be considered treatment emergent unless the CRF data indicates otherwise via explicitly recording time for AE onset and treatment dosing.

Adverse events will be coded using current Medical Dictionary for Regulatory Activities (MedDRA). Severity of AEs will be graded using the NCI-CTCAE v 4.03 toxicity grading scale.

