7.4.1.2. Recording Nonserious AEs and SAEs on the CRF

All nonserious AEs and SAEs occurring in a patient during the active collection period, which begins after obtaining informed consent as described in [Section 9.4](#), will be recorded on the AE section of the CRF.

The investigator is to record on the CRF all directly observed and all spontaneously reported AEs and SAEs reported by the patient.

If a patient begins a new anticancer therapy, the recording period for nonserious AEs ends at the time the new treatment is started; however, SAEs must continue to be recorded on the CRF during the above-indicated active collection period. Note that a switch to a commercially available version of the study treatment is considered as a new anticancer therapy for the purposes of SAE reporting.

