- The investigator is obligated to perform or arrange for the conduct of supplemental measurements and/or evaluations as medically indicated or as requested by the sponsor to elucidate the nature and/or causality of the AE or SAE as fully as possible. This may include additional laboratory tests or investigations, histopathological examinations, or consultation with other healthcare providers.
- New or updated information will be recorded in the originally completed CRF.
- The investigator will submit any updated SAE data to the sponsor within 24 hours of receipt of the information.

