1. VERSION HISTORY

Table 1: Summary of Change

Version/ Date	Associated Protocol Amendment	Rationale	Specific Changes
1.0/ 17 June 2020	2.0/ 13 March 2020	Not Applicable	Not Applicable
2.0/ 18 September 2020	3.0/ 07 August 2020	Updates per protocol amendment v3.0; Pfizer SAP template is used and the standard language and methods included in the Pfizer Oncology Statistics Rulebook are adopted	
 1. General – Added data analysis and summary to address COVID-19 related issues. 2. Section 2 – Added explanation that this version of SAP is based on the outcome of the Safety Lead-in that the high-dose treatment of encorafenib was not included in Phase 2. Therefore no randomization is used in Phase 2. 3. Section 4 – Deleted Per-protocol analysis set. CCI [REDACTED] Minor updates on Safety Set and PK Set. 4. Section 5.2 – Added additional information on general methods per Pfizer Oncology Statistics Rulebook. 5. Section 5.2.5 – Updated on-treatment period definition to include all subsequent anticancer therapies (not just anticancer drug therapy). 6. Section 6.2.5 – Updated PFS censoring reasons and hierarchy per Pfizer Oncology Statistics Rulebook. 7. Section 6.3.1 – Revised the list of PK parameters to be estimated and reported, when feasible and appropriate. CCI [REDACTED] 9. Section 6.6 – Deleted body weight, ECOG PS, dermatologic, ECHO/MUGA and ophthalmic examination data descriptive summary per Pfizer TLFs reduction recommendation. Deleted listing of dermatological examination and physical examination as minimum data are collected for these parameters. CCI [REDACTED] 10. Section 6.6.1 – Added AE summary for patients escalating to 600 mg encorafenib in Phase 2.

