5.2.5. On-treatment Period

On-treatment period is defined as the time from the first dose date of any study drug through (minimum of last dose of study treatment +30 days, start day of subsequent anticancer therapy - 1 day).

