6.5.5. Subsequent Anticancer Therapies/Procedures

Number of patients with any anticancer treatment after discontinuation of study treatment will be summarized by type of therapy (systemic treatment, radiotherapy, and surgery).

Summary statistics will be created for the data collected on the “Subsequent Cancer Treatment Systemic” eCRF page.

Subsequent anticancer systemic treatment will be summarized by ATC class and preferred term and will also be presented in a listing.

Incomplete dates will be handled as described in [Section 5.3.1](#).

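### The TEAE definition has no rule for pre-dose AEs that worsen on drug, and its window ends at a different point from the on-treatment period used for laboratory and ECG tables

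*SAP*

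**What the plan says.** **Start of the window.** SAP 3.4.1 counts an AE as treatment emergent if it begins on or after first dose, and adds: "Any events that started prior to date of the first dose are not considered TEAEs". There is no clause for an increase in grade or seriousness. SAP 6.6.1 bases all AE analyses on this definition unless otherwise specified.

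**How AEs are recorded.** Under protocol 7.4.1, AE collection starts at informed consent, so events with pre-dose onset will exist. Protocol Appendix 7.3 says of follow-up: "New or updated information will be recorded in the originally completed CRF". Protocol Appendix 7.1, however, lists exacerbation of a pre-existing condition, including greater intensity, among the events that are themselves AEs.

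**End of the window.** SAP 3.4.1 closes the TEAE window with: "but before the last dose +30 days, or start of subsequent anticancer *drug* therapy minus 1 day, whichever occurs first". SAP 5.2.5 runs the on-treatment period "through (minimum of last dose of study treatment +30 days, start day of subsequent anticancer therapy - 1 day". The version history records the reason for the wider wording in 5.2.5: "Updated on-treatment period definition to include all subsequent anticancer therapies (not just anticancer drug therapy". SAP 6.5.5 treats radiotherapy and surgery as anticancer treatment; such treatment "will be summarized by type of therapy (systemic treatment, radiotherapy, and surgery".

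**General rule.** SAP 3.4 bases safety summaries on the on-treatment period unless otherwise specified, and says that safety data from outside it are listed and not summarized.

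**The concern.** AE incidence and severity is a secondary endpoint in Phase 2 and a primary endpoint of the Safety Lead-in (SAP 2.1). The AE tables should therefore show what happens on drug, over the same days as the other safety tables. Two features of the SAP work against that.

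- A mild event that begins in screening and becomes severe or serious on drug may or may not reach the tables, depending on how the site enters it. The tables at risk are TEAE incidence, Grade 3 or higher, serious TEAEs, and the AE-term tables for interruption, reduction and discontinuation.
- A patient who stops study drug and then has radiotherapy or surgery has an AE window longer than the laboratory and ECG window. Protocol 7.4.1.2 adds that after a new anticancer therapy "the recording period for nonserious AEs ends at the time the new treatment is started", while SAEs continue to be recorded. If radiotherapy and surgery count as new anticancer therapy there, the extra days would hold mainly SAEs.

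**Working it through.** No figure in the plan needs reproducing; the point rests on definitions.

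**1. Worsening of a pre-dose event.** Take a hypothetical Grade 1 headache starting 10 days before first dose that becomes Grade 3 on study day 20.

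| How the site records it | Onset date in the data | TEAE under SAP 3.4.1? | In Grade 3 or higher table? |
|---|---|---|---|
| Update to the original record (Appendix 7.3) | 10 days before first dose | No | No |
| New AE for the exacerbation (Appendix 7.1) | Day 20 | Yes | Yes |

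The same clinical course gives two different tables, and neither document chooses between the two conventions.

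Size: the documents give no rate for such events. If such a patient has no other event of the same term, the change in that term's incidence is k/N. With N = 50 (one full cohort), k = 1, 2 or 5 gives 2%, 4% or 10%. These values of k are illustrations.

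**2. End of the two windows.** Let day 0 be the last dose, D the start of subsequent drug therapy and R the start of radiotherapy or surgery, omitting whichever does not occur.

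- On-treatment period, last day covered = min(30, D − 1, R − 1). The wording is *through*, so that day is included.
- TEAE window, last day covered = min(30, D − 1) if *before* is read inclusively, and one day less if read strictly. R does not enter.

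| Subsequent therapy | On-treatment, last day | TEAE, last day (strict–inclusive) | TEAE minus on-treatment, days |
|---|---|---|---|
| None | 30 | 29–30 | −1 to 0 |
| Drug on day 14 | 13 | 12–13 | −1 to 0 |
| Radiotherapy or surgery on day 7 | 6 | 29–30 | +23 to +24 |
| Radiotherapy or surgery on day 14 | 13 | 29–30 | +16 to +17 |
| Radiotherapy or surgery on day 21 | 20 | 29–30 | +9 to +10 |
| Radiotherapy on day 7, drug on day 21 | 6 | 19–20 | +13 to +14 |

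The laboratory shift table by maximum grade and the liver summaries (SAP 6.6.3), and the ECG table (SAP 6.6.5), use the on-treatment period. AE tables (SAP 6.6.1) use the TEAE window. In the rows with radiotherapy or surgery, AEs in the extra days qualify for tabulation under 3.4.1, although SAP 3.4 says that data from those days are only listed.

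**3. After alignment.** With the same list of therapies and the same inclusive boundary, the difference is 0 days in every row.

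**The case against.** The best case against the point is that the first gap may never bite. The Appendix 7.3 sentence concerns follow-up information and sets no onset-date rule for a grade increase, whereas Appendix 7.1 makes an exacerbation an AE in its own right. Recorded that way, it already has an on-drug onset and is a TEAE. This stands: the loss is conditional on recording practice, and the CRF completion instructions are not in the documents.

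Several outputs also limit the damage:

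- Events that are not treatment emergent are listed and flagged (SAP 6.6.1).
- Laboratory worsening appears in shift tables and liver categories (6.6.3).
- Dose reductions and interruptions are summarized with reasons from dosing data (6.5.3.1).
- Deaths (6.6.2) and DLTs (6.1.1) have their own tables.

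These points stand too, but listings do not feed incidence tables, and shift tables do not capture symptoms such as headache or nausea.

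On the window, *drug* is emphasized in 3.4.1, so the wording may be deliberate, and 3.4 allows its summary basis to be specified otherwise. That is possible. But the sentence in 3.4 restricting data outside the on-treatment period to listings carries no exception, so the sections still need reconciling.

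A reader might infer that every AE starting before first dose is lost. SAP 5.3.1 does not support this: AEs with a completely missing onset date are generally treated as treatment emergent, and partial onset dates falling in the first-dose month are reset to first dose. The exclusion applies to events with a known pre-dose onset. A reader might also link the gap to escalation to 600 mg. That link is weak: escalation follows Cycle 1, and an event that begins in Cycle 1 is already a TEAE.

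**Conclusion.** Both gaps are in the current SAP text, and both deserve correction before database lock.

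The missing worsening clause creates a risk that on-drug worsening of screening-onset AEs is absent from the main AE tables. Whether it is absent depends on whether sites update the original record or open a new one. Its size cannot be estimated from the documents; the only firm scale is 2 points per affected patient in a cohort of 50, on the assumption stated with the calculation.

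The window mismatch is certain on the wording. It affects patients who have radiotherapy or surgery within 30 days of last dose, by 9 to 24 days for starts between day 7 and day 21. For other patients it is at most a one-day boundary difference. How many patients this concerns is not stated.

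A reader might conclude that the AE tables as a whole undercount toxicity and that both gaps contribute. The documents do not support that. The first gap leads to an undercount only under one recording convention. The second lengthens the AE window after radiotherapy or surgery, so apart from the possible single day it cannot remove events. That any extra days hold mainly SAEs also depends on radiotherapy and surgery counting as new anticancer therapy under protocol 7.4.1.2, which that section does not say.

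**What to change.** 1. In SAP 3.4.1, also count as a TEAE any AE with pre-dose onset that increases in CTCAE grade or becomes serious on or after first dose, within the TEAE window.
2. State how such worsening is identified in the data: either as a new record with its own onset date, or as a dated grade change in the original record. The rule must be consistent with protocol Appendices 7.1 and 7.3 and applied uniformly, including to records already entered. An updated maximum grade without a date of change would not be enough.
3. Define the end of the TEAE window by reference to SAP 5.2.5, with one inclusive boundary, and list later events as SAP 3.4 already provides.

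The cost is a few SAP sentences and a CRF completion note. AE counts may rise slightly from the worsening clause, some events after radiotherapy or surgery move from tables to listings, and existing AE records may need review so that early and late entries are treated alike.

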3.4.2. Laboratory Data

Hematology, chemistry and coagulation tests results will be programmatically graded according to the NCI CTCAE version 4.03 for relevant parameters. Additional details are provided in [Section 6.6.3](#).

3.4.3. Vital Signs Data

Vital signs data includes weight, pulse, systolic blood pressure (BP), and diastolic BP will be summarized. Additional details are provided in [Section 6.6.4](#).

3.4.4. Electrocardiograms Data

Clinically notable ECG values during the on-treatment period will be summarized. Additional details are provided in [Section 6.6.5](#).

4. ANALYSIS SETS (POPULATIONS FOR ANALYSIS)

Data for all patients will be assessed to determine if patients meet the criteria for inclusion in each analysis population prior to releasing the database and classifications will be documented per standard operating procedures.

Patient Analysis Set	Description
Enrolled	All patients who sign the informed consent form (ICF). Potential participants who are screened for the purpose of determining eligibility for the study, but do not participate in the study, are not considered enrolled.
Dose-determining Set	All patients enrolled in the high-dose treatment arm in the Safety Lead-in who complete one 28-day cycle of treatment and receive at least 75% of the planned cumulative dose of both study drugs or discontinue treatment because of DLT.
Full Analysis Set (FAS)	The FAS includes all patients who receive at least 1 dose of any study drug in the Phase 2 portion of the study.
Efficacy Set	
The Efficacy Set includes all FAS patients who receive at least 1 dose of any study drug in the Phase 2 portion of the study and have their BRAFV600 mutation status confirmed by central laboratory.
 
Unless otherwise specified, the Efficacy Set will be the default analysis set used for all efficacy analyses.

Safety Set	The Safety Set includes all patients who receive at least 1 dose of any study drug. Unless otherwise specified, the Safety Set will be the default analysis set used for all safety analyses.
PK Set	The PK Set includes all patients who receive at least 1 dose of any study drug and have at least 1 PK blood collection after the first dose of study drug with associated bioanalytical results. The PKS will be used for summaries and listings of PK data.
CCI	[REDACTED]

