6.6. High-dose Safety Assessment

After 9 evaluable patients in the Safety Lead-in have completed one 28-day cycle of treatment, safety assessments will be conducted. All toxicities will be assessed for severity by the Investigator using CTCAE v4.03. Evaluable patients for the Safety Lead-in cohort must have either:

- experienced a DLT (Table 7) or
- received at least 75% of the planned cumulative dose of both study drugs during Cycle 1.

The Sponsor and participating Investigators will perform ongoing reviews of patient safety data through regular teleconferences approximately weekly during the Safety Lead-in. Once 9 evaluable patients are available for assessment, the Sponsor will convene a joint teleconference with participating Investigators. If the high-dose treatment is found safe based on 9 evaluable patients, subsequent patients will be randomized 1:1 to receive either the standard or high-dose treatment. If the high-dose treatment is determined not to be safe, enrollment will proceed with the standard-dose treatment as outlined in Section 4.1. The high-dose treatment will be considered safe if the rate of DLTs (Table 7) observed in the first cycle of treatment in the Safety Lead-in is $< 33\%$.

Table 7. Criteria for Defining Dose-limiting Toxicities

DLT Definition
A DLT is defined as any AE or laboratory abnormality that is not explained by underlying disease, disease progression, intercurrent illness, or concomitant therapies that either meets the criteria described below or results in the inability to tolerate at least 75% of the planned dose of binimetinib or encorafenib during Cycle 1.
Specific DLT Criteria
Cardiac disorders 
 • Absolute decrease of LVEF > 10% compared to baseline and the LVEF is below the institution's LLN • LV systolic dysfunction Grade ≥ 3 • Other cardiac disorders Grade ≥ 3
Vascular disorders 
 • Grade 3 hypertension for > 14 consecutive days • Grade 4 hypertension
Skin and subcutaneous tissue disorders^a 
 • Rash, hand foot skin reaction (HFSR) or photosensitivity CTCAE Grade 3 for > 14 consecutive days despite maximal skin toxicity treatment (as per local practice) • Rash, HFSR or photosensitivity CTCAE Grade 4

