6.11. Replacement of Patients

Patients may be replaced for any of the following reasons:

- During the Safety Lead-in, any patient who receives < 75% of the planned cumulative dose of either encorafenib or binimetinib during Cycle 1 for any reason other than a DLT (e.g., not evaluable for a DLT [Table 7]) may be replaced to ensure a minimum number of evaluable patients.
- Patients who do not meet the eligibility requirements of the study may be replaced.
- Patients for whom the *BRAFV600* mutation status is not confirmed by central laboratory may be replaced. This includes either an Indeterminate or a No Mutation *BRAFV600* Detected result.

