8.4.1. Primary Analyses

Safety Lead-in

The number and proportion of patients in the Dose-determining Set experiencing DLTs during the first treatment cycle in the Safety Lead-in will be summarized. Safety and exposure data will be summarized as described in the SAP.

Phase 2

The primary endpoint in the Phase 2 portion of the study is BMRR per mRECIST v1.1. It is defined as the proportion of patients who have achieved a best overall brain metastasis response of CR or PR according to mRECIST v1.1 per Investigator assessment. Details of best overall brain metastasis response are specified in [Appendix 5](#).

Both confirmed and unconfirmed BMRR will be summarized, but the primary analysis will be based on confirmed responses.

The primary analysis will take place after all patients in the Efficacy Set have had the opportunity for at least 2 post-baseline tumor assessments, and after all patients with an initial response have had an opportunity to be followed up for at least 6 months.

The BMRR will be calculated with an exact two-sided 90% CI. In addition, the exact two-sided 95% CI of BMRR will also be calculated.

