5.1.1.1. Safety Lead-in

There is no statistical hypothesis for the Safety Lead-in.

The primary endpoint of the Safety Lead-in is incidence of DLTs. Up to 9 evaluable patients will be enrolled to receive the high-dose encorafenib + binimetinib combination therapy. The safety and PK data will be evaluated by the Steering Committee after these 9 evaluable patients have been followed for a minimum of 28 days.

5.1.1.2. Phase 2

The sample size calculation is based on the primary endpoint of BMRR per mRECIST v1.1 by Investigator assessment. The study is designed to test the null hypothesis of $BMRR \leq 30\%$ for patients with *BRAFV600*-mutant melanoma brain metastasis, which is considered not sufficiently clinically meaningful to warrant further study. The alternative hypothesis is $BMRR > 30\%$ with the assumption that the true BMRR is at least 50%.

If the high-dose treatment is determined not to be safe in the Safety Lead-in, no patients will be enrolled into the high-dose treatment arm. Up to 100 eligible patients will be enrolled into 2 cohorts in the standard-dose treatment arm. Phase 2 enrollment will close when either Cohort 1 or 2 reaches the enrollment of 50 patients. The sample size consideration is based on an exact binomial test with a 1-sided alpha of 0.05 for each cohort.

- **Cohort 1:** Patients with locally confirmed *BRAFV600* cutaneous melanoma with metastases to the brain confirmed by MRI, asymptomatic, and *with* prior local therapy (eg, SRS or SRT).
- **Cohort 2:** Patients with locally confirmed *BRAFV600* cutaneous melanoma with metastases to the brain confirmed by MRI, asymptomatic, *without* prior local therapy (eg, SRS or SRT).

No formal statistical comparison will be conducted between the 2 cohorts.

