6.1. Primary Endpoints

6.1.1. Safety Lead-in

The number and proportion of patients experiencing DLTs during Cycle 1 will be summarized by SOC and PT based on maximum toxicity grade. Analyses of DLT will be performed on Dose-determining Set.

All DLTs and their attributes will be presented in data listings sorted by patient identifier, AE and date of onset of the AE.

6.1.2. Phase 2

Main Analysis:

BMRR will be calculated by dividing the number of patients with a BOR of confirmed CR or confirmed PR in brain metastasis by the number of patients in the Efficacy Set in the respective cohort. The corresponding exact Clopper-Pearson 2-sided 90% CI and 95% CI will be calculated.

BOR is defined as the best response recorded from date of the first dose of study treatment until progression by Investigator assessment at each time point. Only tumor assessments performed before the start of any subsequent anticancer therapies will be considered in the assessment of BOR. Clinical deterioration or clinical progression noted on the End of Study completion eCRF will not be considered as documented disease progression. BOR will be determined according to the following rules:

- CR = at least two determinations of CR at least 4 weeks apart and documented before progression and start of new anticancer therapy.
- PR = at least two determinations of PR or better (and not qualifying for a CR) at least 4 weeks apart and documented before progression and start of new anticancer therapy.
- SD (for patients with at least one measurable lesion at baseline)= at least one SD assessment (or better and not qualifying for CR or PR) ≥ 6 weeks after date of the first dose and before progression and start of new anticancer.
- Non-CR/Non-PD (for patients with only non-target disease at baseline) = at least one Non-CR/Non-PD assessment (or better and not qualifying for CR or PR) ≥ 6 weeks after date of the first dose and before progression and the start of new anticancer therapy.
- PD = progression ≤ 16 weeks after date of the first dose (and not qualifying for CR, PR or SD).
- Not Evaluable (NE) = all other cases.

The frequency (number and percentage) of patients with BOR in brain metastasis of CR, PR, SD, PD, non-CR/non-PD (applicable only to patients with non-measurable disease at baseline), and NE will be tabulated.

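### The Dose-determining Set can leave out a Lead-in patient with a DLT whom Protocol 6.6 counts as evaluable, so the primary DLT table may not reproduce the recorded 3 of 9

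*SAP*

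**What the plan says.** **Who is evaluable.** Protocol 6.6 states "Evaluable patients for the Safety Lead-in cohort must have either" had a DLT or taken 75% or more of both drugs in Cycle 1. The synopsis (1.1) and section 4.1 say the same. Stopping treatment is not required. The replacement rule in Protocol 6.11 agrees: it covers a Lead-in patient who "receives < 75% of the planned cumulative dose of either encorafenib or binimetinib during Cycle 1 for any reason other than a DLT", so a patient below 75% because of a DLT is not replaced on that ground.

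**What a DLT is.** Besides the listed toxicities, Table 7 of the protocol includes an event that "results in the inability to tolerate at least 75% of the planned dose of binimetinib or encorafenib during Cycle 1".

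**Who is analysed.** The Dose-determining Set has the same definition in SAP 4 and Protocol Table 15: high-dose Lead-in patients who complete one 28-day cycle and "receive at least 75% of the planned cumulative dose of both study drugs or discontinue treatment because of DLT". Protocol 8.4.1 summarises "The number and proportion of patients in the Dose-determining Set experiencing DLTs during the first treatment cycle". SAP 6.1.1 says "Analyses of DLT will be performed on Dose-determining Set". SAP 3.1.1 bases the endpoint on DLT-evaluable patients but does not define them.

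**What was recorded.** SAP 2 reports 3 DLTs in 9 evaluable patients and, on that basis, no high-dose arm in Phase 2.

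**The concern.** The evaluability rule asks whether a DLT occurred. The analysis set asks whether treatment was discontinued because of it. These are different conditions, and a patient can meet one without the other.

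DLT incidence is a primary endpoint of the Lead-in. On the DLT route, an exclusion removes the patient from both numerator and denominator, so the reported rate can only fall. The observed count sits exactly on the decision boundary, so a single exclusion moves the table to the other side of the criterion and makes it appear to contradict the decision in SAP 2. The Lead-in brain metastasis response rate (Protocol 8.4.2.7, SAP 6.2.7) and the Lead-in baseline summaries (SAP 6.5.1) use the same set.

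The definition also leaves several readings open, to be settled after the DLTs are known.

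**Working it through.** **1. The plan's own figures.** Protocol Table 14 and SAP Table 2 give the probability of at least 3 DLT patients in 9. The formula is P(X ≥ 3) = 1 − Σ C(9,x) p^x (1−p)^(9−x), summed over x = 0 to 2. For p = 10, 20, 30, 40 and 50% it gives 0.0530, 0.2618, 0.5372, 0.7682 and 0.9102, against the stated 0.053, 0.262, 0.537, 0.768 and 0.910. The 3 + 3 column, 1 − [(1−p)^3 + 3p(1−p)^2(1−p)^3], also matches. These figures describe 9 evaluable patients in whom every DLT counts. They describe the Dose-determining Set only if no DLT patient is left out.

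**2. The two definitions side by side.**

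| Patient with a Cycle 1 DLT | Evaluable (6.6) | In the set (SAP 4) |
|---|---|---|
| Completes the cycle with ≥ 75% of both drugs | Yes | Yes |
| Stops both drugs permanently because of the DLT | Yes | Yes, if the DLT route stands alone |
| Below 75%, held, then resumes | Yes | (i) No, if discontinuation means permanent; yes, if temporary stops count |
| Below 75% through reduction alone | Yes | (ii) No, even if temporary stops count |
| Stops binimetinib alone, below 75% of it | Yes | (iii) No, if treatment means the combination |

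The protocol uses discontinuation for temporary stops in 7.4.1 and Appendix 10 (10.10.6), so the text does not settle (i). For (iii), retinal vein occlusion is a DLT in Table 7, Appendix 3 stops binimetinib only, and 6.7.1 permits single-agent encorafenib. SAP 6.5.3 then dates the end of treatment by the last encorafenib dose.

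**3. Can such patients fall below 75%?** One level down in Table 8 is 225/300 = 0.75 for encorafenib and 30/45 = 0.667 for binimetinib. Share of the planned 28-day dose received:

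- Row (i), 14 full-dose days, 7 held, 7 one level down: encorafenib (14 + 0.75 × 7)/28 = 68.8%; binimetinib (14 + 0.667 × 7)/28 = 66.7%.
- Row (ii), one level down after d full-dose days with no hold: encorafenib (d + 0.75 × (28 − d))/28 is never below 75.0%. Binimetinib (d + 0.667 × (28 − d))/28 is 73.8% at d = 6 and 75.0% at d = 7, so it is below 75% only if d < 7.
- Row (iii), binimetinib stopped after d days: d/28 = 50.0% at d = 14, 71.4% at d = 20 and 75.0% at d = 21.

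**4. Effect on the reported rate.** Assumption: the 3 DLTs are in 3 patients, since the rule in Protocol 8.2 counts patients. With k of them left out, the rate is (3 − k)/(9 − k), with Clopper-Pearson 95% limits:

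| k | Rate | 95% CI |
|---|---|---|
| 0 | 3/9 = 33.3% | 7.5% to 70.1% |
| 1 | 2/8 = 25.0% | 3.2% to 65.1% |
| 2 | 1/7 = 14.3% | 0.4% to 57.9% |
| 3 | 0/6 = 0% | 0% to 45.9% |

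**5. Effect on the operating characteristics.** Suppose each DLT patient is left out with probability q, a figure the documents do not give. At a true DLT rate of 40%, the chance that the rate in the set reaches one third is 0.768 for q = 0, 0.687 for q = 0.10, 0.555 for q = 0.25 and 0.337 for q = 0.50.

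**The case against.** The strongest reply is that few patients are exposed and nothing turns on the table.

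- **Temporary stops.** If these count, the gap nearly closes. The reduction rules in Appendices 2 and 3 start with a hold. The renal rule in 6.7.3, which states none, concerns encorafenib, where one level down never falls below 75%. This is fair, but it depends on a reading the SAP does not state.
- **One drug or both.** Protocol 6 defines study treatment as any of the investigational drugs, and the SAP's adverse event tables treat discontinuation drug by drug. Stopping binimetinib alone can therefore be read as qualifying. Retinal vein occlusion is also rare, at 0.1% in Protocol 2.2.3. Case (iii) is plausible but thin.
- **Grade 4 events.** Protocol 6.8 has these patients discontinue, so most enter through the DLT route. That narrows case (i) mainly to DLTs below Grade 4 that are held and resumed, a course Protocol 6.7.1 and Appendix 2 provide for.
- **The unbracketed and/or.** Applying cycle completion to the DLT route would defeat that route's purpose, so this reading is unlikely. Brackets still cost nothing.
- **The opposite direction.** The 28-day condition can also exclude a non-DLT patient. One who stops at day 22 on full dose has 22/28 = 78.6% and is evaluable under the second route of 6.6, but falls outside the set, giving 3/8 = 37.5%. This is true of the definition as a whole; the fall described here concerns the DLT route only.
- **Visibility.** SAP 6.1.1 lists all DLTs, Safety Set tables show the events, there is no Lead-in hypothesis, and the decision is already recorded. All of this stands and limits the harm. It does not make the primary table agree with the decision.

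**Conclusion.** The concern holds. The analysis set for a primary endpoint uses a narrower DLT condition than the evaluability rule that drove the decision, and reading (i) survives every objection. If one DLT patient is excluded, the reported rate goes from 33.3% to 25.0%; the full range is 33.3% down to 0%. This is conditional arithmetic, not an expectation. It assumes that the 3 DLTs are in 3 patients, and the documents do not say whether any of the 9 is affected. The decision not to open the high-dose arm was taken on 9 evaluable patients and does not change. What is at risk is a primary table that cannot be reconciled with that decision, so the definition should be fixed before patients are classified for database release.

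**What to change.** In SAP 4, define the Dose-determining Set as all Lead-in patients who either (a) finish the 28-day cycle having taken at least 75% of each drug's planned cumulative dose, or (b) have a DLT during Cycle 1. Bracket (a) and (b) so that (b) stands alone. Have SAP 3.1.1 name this set as its DLT-evaluable patients.

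Keep the 28-day condition in (a). It has support in Protocol 6.6 ("After 9 evaluable patients in the Safety Lead-in have completed one 28-day cycle of treatment, safety assessments will be conducted") and in SAP 5.1.1.1, which times the data review "after these 9 evaluable patients have been followed for a minimum of 28 days". The two-part list in 6.6 omits the condition, so the two should be reconciled.

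Carry the wording into Protocol Table 15 at the next amendment; it need not prompt one, since Protocol 9.1 requires authority approval before an amendment is implemented. If the SAP is not revised, add a footnote to the primary DLT table giving the number of Cycle 1 DLT patients outside the set.

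The cost is one sentence and one cross-reference, with no new data.
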